## **2. TRIAL OBJECTIVES AND ENDPOINTS**

### **2.1 MAIN OBJECTIVES, PRIMARY AND SECONDARY ENDPOINTS**

#### **2.1.1 Main Objectives**

The main objective is to assess long term safety of treatment with oral nintedanib in patients with Systemic Sclerosis associated Interstitial Lung Disease (SSc-ILD).

#### **2.1.2 Primary Endpoint(s)**

The primary endpoint is the incidence (number and % of patients) of overall adverse events over the course of this extension trial.

#### **2.1.3 Secondary Endpoint(s)**

Not applicable.

### 3. DESCRIPTION OF DESIGN AND TRIAL POPULATION

#### 3.1 OVERALL TRIAL DESIGN AND PLAN

This is a multi-centre, multi-national, prospective, open label extension clinical trial. It is anticipated that approximately 400 patients with SSc-ILD will complete the parent trial SENSISCIS® and approximately 14 patients will complete 1199-0340 as planned. These patients will be eligible for enrolment in this extension trial. Patients who withdrew treatment prematurely in SENSISCIS® / 1199-0340 will not be eligible for this open label extension trial.

After signing Informed Consent and if all eligibility criteria are met, patients will initiate treatment with nintedanib (Visit 2). Patients will be assigned to a dose of 150 mg bid if the patients last dose in SENSISCIS® / 1199-0340 was 150 mg bid and to a dose of either 100 mg bid or 150 mg bid at the discretion of the investigator, if patients were on 100 mg bid of blinded trial medication in SENSISCIS® / 1199-0340 (please refer to [Section 4.1.2](#)).

Once assessment of the pivotal trial SENSISCIS® and resulting risk-benefit of Nintedanib has been concluded upon, patients that are on a reduced dose of trial medication may increase dose to 150 mg bid Nintedanib at the discretion of the investigator.

The trial will continue for long term data collection, as long as a reasonable number of patients enabling analyses remain in the trial. Treatment duration for each patient will be variable. Patients will continue to receive treatment until they meet a reason for discontinuation (refer to [section 3.3.4.4](#)) or until access to nintedanib is obtained outside the clinical trial. The trial is estimated to last a total of approximately 5 ½ years.

Treatment will be stopped if a reason for withdrawal is met (refer to [Section 3.3.4](#)).

[figure not shown]

Figure 3.1: 1 Transition from parent trial SENSISCIS® / 1199-0340

### 3.2 DISCUSSION OF TRIAL DESIGN, INCLUDING THE CHOICE OF CONTROL GROUP(S)

The trial will be conducted as a prospective, open-label design. This design is appropriate for this rollover trial assessing the long-term safety on nintedanib in patients with SSc-ILD.

The purpose of this trial is to offer to all patients who completed SENSISCIS® / 1199-0340 as planned, the option to receive nintedanib treatment if they perceive an individual benefit. The decision to continue treatment will be made by the patient following a discussion with the investigator. The aim of the trial is to allow treatment continuation to individual patients; therefore, randomization, blinding and use of placebo would not be appropriate.

The planned assessments are a subset of the assessments done in SENSISCIS® / 1199-0340 and an additional patient related outcome score to assess gastrointestinal symptoms and their impact on the patient.

### 3.3 SELECTION OF TRIAL POPULATION

It is anticipated that approximately 400 patients will complete the SENSISCIS® trial on treatment with nintedanib or placebo and that approximately 14 patients will complete the 1199-0340 trial. These patients will be allowed to participate in this open label extension trial. At the time point of the start of the open label extension trial it is not known what treatment the patients had received in SENSISCIS®. Patients previously on active treatment will continue, patients who received placebo will initiate treatment with nintedanib for the first time at Visit 2 of the extension trial. Patients who completed 1199-0340 had open-label treatment with nintedanib and will continue with nintedanib treatment in 1199.225.

A log of all patients enrolled into the trial (i.e. who have signed informed consent) will be maintained in the ISF at the investigational site irrespective of whether they have been treated with investigational drug or not.

#### 3.3.1 Main diagnosis for trial entry

Patients with SSc-ILD will be included in this trial if they fulfil all the inclusion and do not present any of the exclusion criteria.

Only patients who have completed the SENSISCIS® / 1199-0340 on treatment (i.e. did not early permanently discontinue blinded treatment) are eligible. Patients should enrol into the extension trial as soon as possible after conclusion of SENSISCIS® / 1199-0340.

Please refer to [Section 8.3.1](#) (Source Documents) for the documentation requirements pertaining to the in- and exclusion criteria.

#### 3.3.2 Inclusion criteria

1. Patients who completed the SENSISCIS® / 1199-0340 trial per protocol and did not permanently discontinue study treatment

2. Signed and dated written informed consent in accordance with ICH-GCP and local legislation prior to admission to the trial
3. Women of childbearing potential must be ready and able to use highly effective methods of birth control per ICH M3 (R2) that result in a low failure rate of less than 1% per year when used consistently and correctly as well as one barrier method for 28 days prior to nintedanib treatment initiation, during the trial and for 3 months after last intake of nintedanib. A list of contraception methods meeting these criteria is provided in the patient information.

9. Usage of any investigational drug after completion of SENCIS® / 1199-0340, or planned usage of an investigational drug during the course of this trial.
10. A disease or condition which in the opinion of investigator may put the patient at risk because of participation in this trial (e.g. clinically relevant intestinal pseudoobstruction) or limit the patient's ability to participate in this trial
11. Chronic alcohol or drug abuse or any condition that, in the investigator's opinion, makes them an unreliable trial subject or unlikely to complete the trial
12. Known hypersensitivity to the trial medication or its components (i.e. soya lecithin).
13. Women who are pregnant, nursing, or who plan to become pregnant while in the trial
14. Previous enrolment in this trial

### **3.3.4 Withdrawal of patients from therapy or assessments**

#### **3.3.4.1 Withdrawal from trial treatment**

Nintedanib has to be permanently discontinued in the following circumstances

- The patient experiences signs of hepatic injury, defined in [Section 4.2.1.2](#)
- In the opinion of the investigator, the patient experiences unacceptable adverse events despite dose adjustments and supportive care.

- Use of concomitant treatment as defined in [Section 4.2.2](#).
- Parenteral feeding requirement.
- The patient can no longer be treated with trial medication for other medical reasons
- The patient has repeatedly shown to be non-compliant with important trial procedures and, in the opinion of both, the investigator and sponsor representative, is not willing or able to stick to the trial requirements in the future
- Pregnancy (refer to [Section 5.2.11](#))
- If a patient becomes pregnant during the trial, nintedanib needs to be stopped and the patient should be followed up until birth or otherwise termination of the pregnancy. The data of the patient will be collected and reported in the clinical trial report (CTR) until patient's last visit and any events thereafter will be reported in the BI drug safety database. Refer to [Section 5.2.11](#) for detailed information on event reporting in case of pregnancy.

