4.2.1.2 Management of liver enzyme elevation

Evaluate the concomitant use of other drugs known to cause liver enzyme elevations. For a detailed guidance on how to manage liver enzyme elevations, please refer to Table [4.2.1.2: 1](#).

Table 4.2.1.2: 1: Management of liver enzyme elevations

	AST or ALT increase to			Signs of hepatic injury* ( Section 5.2.11 )
	>1.5x to <3x ULN	≥3x to <5x ULN and no signs of hepatic injury ( Section 5.2.11 )	≥5x to <8x ULN and no signs of hepatic injury ( Section 5.2.11 )	
Visit 2 (treatment start )	Continue as planned 	Permanently discontinue trial medication	Permanently discontinue trial medication	Permanently discontinue trial medication
Any other Visit	Continue as planned 	Reduce dose or interrupt trial medication 	Interrupt trial medication	Permanently discontinue / Interrupt trial medication
		Close observation   After 2 weeks or any time later	Close observation   After 2 weeks or any time later	CLINICAL EVALUATION OF HEPATIC INJURY ( Section 5.2.11 )
	<3x ULN	≥3x ULN	< 3x ULN	
	Reduced: return to initial dose.  Interrupted: restart at reduced dose. Monitor every 2 weeks for at least 8 weeks	Permanently discontinue trial medication  Close observation 	Restart at reduced dose  Monitor weekly for 4 weeks, then every 2 weeks for at least 8 weeks	Permanently discontinue trial medication.  Close observation 

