**Footnotes:**

\* Signs of hepatic injury are defined as

- ALT and/or AST ≥8 fold ULN
- ALT and/or AST ≥3 fold ULN and total bilirubin ≥2 fold ULN
- ALT and/or AST ≥3 fold ULN and unexplained INR >1,5
- ALT and/or AST ≥3 fold ULN and unexplained eosinophilia (>5%)
- ALT and/or AST ≥3 fold ULN and appearance of fatigue, nausea, vomiting, right upper abdominal quadrant pain or tenderness, fever and/or rash

 Investigator to confirm in writing that continuation is justified (e.g. intermittent fluctuation of transaminases).

 According to visit schedule. Consider additional control visits as adequate.

 To be decided by investigator, based on individual risk assessment.

 Close observation: Re-test ALT and AST, alkaline phosphatase, total bilirubin, and eosinophils within 48 to 72 hours, then approximately 7 days, then approximately 2 weeks by using intermediate visit lab kit.

 If clear evidence for alternative cause for hepatic injury was identified and resolved (i.e. relation to trial medication excluded, hepatic injury confirmed to have alternative explanation [other than use of IMP]): return to trial medication would be possible, after consultation with the sponsor. Prior to restart, liver laboratory values must be normal. Monitor weekly for first 4 weeks of re-introduction and every 2 weeks for the following 8 weeks.

Initial assessment and blood sampling for liver enzyme elevation follow up should be performed at the investigational site. Blood samples for additional monitoring may be collected at the investigational site, primary care physician or external laboratory with specific trial lab kits and sent to the central laboratory for analysis.

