#### Hepatic injury

In this trial protocol, signs of hepatic injury are defined as:

- ALT and/or AST  $\geq 8$  fold ULN
- ALT and/or AST  $\geq 3$  fold ULN and total bilirubin  $\geq 2$  fold ULN\*

- ALT and/or AST  $\geq 3$  fold ULN and unexplained INR  $> 1,5^*$
- ALT and/or AST  $\geq 3$  fold ULN and unexplained eosinophilia ( $>5\%$ )\*
- ALT and/or AST  $\geq 3$  fold ULN and appearance of fatigue, nausea, vomiting, right upper abdominal quadrant pain or tenderness, fever and/or rash

\* in the same blood draw sample.

These lab findings constitute a hepatic injury alert and the patients showing these lab abnormalities need to immediately stop the trial medication and need to be followed up according to the “drug-induced liver injury (DILI) checklist” provided in the ISF.

In case of clinical symptoms of hepatic injury (icterus, unexplained encephalopathy, unexplained coagulopathy, right upper quadrant abdominal pain, etc.) without lab results (ALT, AST and total bilirubin) available, the investigator should make sure these parameters are analysed, if necessary in an unscheduled blood test. Should the results meet the criteria of hepatic injury alert, the procedures described in the DILI checklist should be followed.

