	B2	Informed consent given too late	CRF date of informed consent is after date of Visit 1. Signature of the wrong Informed Consent version, and later signature of the correct one will also be part of this IPD category Manual IPD	None
	B3	Informed consent not given or withdrawn for biobanking but biobanking done	According to database and CRF page informed consent for biobanking Automatic IPD	None
C		Trial medication and randomisation		
	C1	Incorrect trial medication taken	Wrong medication number. Medication kit assigned at visit 2 does not match treatment dose actually received by patient Automatic IPD	None
	C2	Trial medication not interrupted (or interruption done too late) when ALT or AST ≥ 5 fold ULN	Based on liver enzyme elevation and interruptions reported during the trial Manual IPD	None

Table 6.2: 1 Important protocol deviations (cont'd)

Category/Code	Description	Requirements	Excluded from
C3	Trial medication not permanently discontinued after signs of liver enzyme elevations were observed that a) are indicative of hepatic injury as defined in Section 5.4.4 b) correspond to ALT or AST \geq 3 fold ULN despite dose reduction or treatment interruption for 2 weeks or more	All patients where signs of liver enzyme elevations are not dealt with according to the requirements of the CTP and no confirmed alternative cause found (as confirmed by BI medicine) for the potential drug-induced liver injury (DILI) event. Manual IPD based on review of MORM listings	None
D	Concomitant Medication		
D1	Patient received prohibited concomitant therapies (see Section 4.2.2.1 of the CTP)	Investigational therapies are not allowed Review of MORM listings and / or to be identified at the site level on the manual PD log.	None
E	Missing data		
E1	Patient without any physical assessment for more than 6 months although under study medication	Prior to the start of COVID-19 disruption, no vital signs $>$ 6 months. After the start of COVID-19 disruption, no vital signs or local labs $>$ 6 months. Manual IPD	None
E2	Flow chart not observed for the planning of visit 1 and 2	Visit 1 and Visit 2 occurred on the same date whereas the period between last available laboratory test within SENCIS™ or 1199-0340 and Visit 2 of the extension trial (1199.225) is $>$ 6 weeks (i.e. \geq 7 weeks) Automatic IPD	None

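### After Visit 2, Protocol Section 3.3.4.1 requires a permanent stop for signs of hepatic injury without exception, while the liver table and its footnote 5 allow interruption and a conditional return to drug

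*Protocol*

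**What the plan says.** Protocol Section 3.3.4.1 opens its list of mandatory stops with "Nintedanib has to be permanently discontinued in the following circumstances". The first item is "The patient experiences signs of hepatic injury, defined in" Section 4.2.1.2. No exception is given, and Section 4.2.1.2 is cited as the place where the signs are defined.

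Table 4.2.1.2:1 has a column for signs of hepatic injury. At Visit 2 the only action is permanent discontinuation. At any other visit the action is "Permanently discontinue / Interrupt trial medication". Beneath that cell stands a clinical evaluation step marked with footnote 5. The footnote begins "If clear evidence for alternative cause for hepatic injury was identified and resolved", asks that a relation to trial medication be excluded, and then says "return to trial medication would be possible, after consultation with the sponsor". It adds "Prior to restart, liver laboratory values must be normal".

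Protocol Section 5.2.11.1 says that patients with these findings "need to immediately stop the trial medication", without saying whether the stop is permanent.

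In the SAP, Section 6.2, deviation C3 is described as "Trial medication not permanently discontinued after signs of liver enzyme elevations were observed". Its requirements column counts a case only if it was not handled as the protocol requires and no alternative cause was confirmed by the sponsor's medical function.

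**The concern.** Hepatic injury is one of two adverse events of special interest named in Protocol Section 5.2.11.1, so its stopping rule should read the same wherever a site looks. It does not, and Protocol Section 5.2.3 sends investigators to both places: Section 4.2.1.2 for monitoring elevations and Section 3.3.4 for withdrawal criteria.

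The two outcomes have different consequences. Permanent discontinuation leads to the End of Treatment visit, which Section 6.2.3 makes the trial completion visit, and exclusion criterion 14 bars re-enrolment. An interrupted patient stays in the trial.

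The SAP also treats the outcomes differently. Time to permanent discontinuation and time to first interruption are separate variables (Sections 5.4.6 and 7.7), and adverse events leading to each go in separate tables (Section 7.8.1).

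**Working it through.** The plan gives no figure on this point and no arithmetic applies. The check sets the provisions side by side and follows three kinds of patient through them.

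| Provision | Action on signs of hepatic injury | Route back to drug |
|---|---|---|
| Protocol 3.3.4.1 | Permanent stop | None stated |
| Table 4.2.1.2:1, Visit 2 | Permanent stop | None stated in the cell |
| Table 4.2.1.2:1, any other visit | Permanent stop or interruption; no criterion in the cell | Clinical evaluation, then footnote 5 |
| Footnote 5 | Applies after the evaluation | Yes: clear alternative cause, resolved; drug relation excluded; sponsor consulted; liver values normal |
| Protocol 5.2.11.1 | Immediate stop, duration not stated | Not addressed |
| SAP 6.2, C3 | Non-discontinuation is a deviation | Not counted if an alternative cause is confirmed |

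**Patient A, signs at Visit 2.** Section 3.3.4.1 and the Visit 2 cell give the same action. There is no conflict.

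**Patient B, signs at a later visit, no clear alternative cause.** Section 3.3.4.1 gives a permanent stop. The cell lets the site begin with an interruption, but footnote 5 then offers no way back. The patient is off drug from the alert and stays off under either text. Only the label given to the first action can differ.

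**Patient C, signs at a later visit, every footnote 5 condition met.** Section 3.3.4.1 still gives a permanent stop. Footnote 5 allows a return to drug. Here the final outcome depends on which text the site follows.

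For Patient C the analysis differs as follows.

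- Under a permanent stop, the patient is an event for time to permanent discontinuation at that point. Adverse event time at risk, for events not yet experienced, ends no later than last intake plus 7 days (SAP Section 7.8.1.5).
- Under interruption and restart, the patient is an event for time to first interruption if it is the first. Duration of exposure runs on without subtracting the gap (SAP Section 5.4.3), the off-treatment days count as on-treatment for safety (SAP Section 6.1), and later adverse events are still counted.
- In the deviation listing, a site that restarts Patient C under footnote 5 departs from the literal text of Section 3.3.4.1 but is not counted under C3.

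Protocol Section 1.4 contains both kinds of wording in general terms. It is a summary not tied to the five defined signs, so the point does not rest on it.

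**The case against.** The best reply is that this is only a missing cross-reference. Section 3.3.4.1 links to Section 4.2.1.2, so the reader reaches the table and its footnote. Section 3.3.4.2 ends by pointing to Section 4.2.1 for conditions that allow interruption. Table 4.2.1:1 separates drug-related from unrelated events. Read together, the natural sense is to stop, evaluate, and return only under the narrow exception.

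That may well be what was intended, but it does not remove the conflict. The link in Section 3.3.4.1 is for the definition of the signs, not for an exception to the rule. The interruption pointer stands under Section 3.3.4.2, which lists recommended stops that leave the investigator discretion, whereas hepatic injury is on the mandatory list. Followed anyway, the pointer leads to the same two-action cell.

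What does stand is the limit on size. A reader might infer more than the documents support:

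- That every patient with any of the five signs is affected. Patient A is not, and Patient B ends permanently off drug either way.
- That a site may keep dosing, or restart on its own authority. No provision for these signs continues drug at the alert, and restart needs sponsor consultation and normal liver values.
- That C3 contradicts itself. Its description names the deviation and its requirements column says when it counts. The alternative-cause exception there is in line with footnote 5, and the review is manual.
- That the liver is the main organ risk. Protocol Section 1.2 names gastrointestinal and liver risks together, and Section 1.4 describes the risks as primarily gastrointestinal.

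**Conclusion.** The inconsistency is real and should be corrected. For signs of hepatic injury after Visit 2, the protocol states one rule with no exception and another with a conditional exception.

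Its reach is the group of patients who meet every footnote 5 condition. The documents give no expected number and none can be derived from them. For those patients the choice of text decides whether they leave the trial and on which side of the discontinuation and interruption summaries they fall. For other patients with signs after Visit 2, the cell leaves the first action open but the final outcome is the same.

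No test or confidence statement is at risk, because Protocol Section 7.2 plans no formal inference, and no deviation removes a patient from analysis (SAP Section 6.2).

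The conclusion assumes that Section 3.3.4.1 is read as written and that footnote 5 is the only route back after signs of hepatic injury. If the sponsor intended Section 3.3.4.1 to include footnote 5, the remedy is only to say so there.

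**What to change.** Reconcile Protocol Section 3.3.4.1, the hepatic injury cell of Table 4.2.1.2:1 for visits other than Visit 2, and footnote 5, so that all three state one rule. The rule should say whether an alternative-cause exception exists, when it applies, and, if the cell keeps two actions, what decides between them at the alert. Check that the immediate stop in Section 5.2.11.1 agrees with it. The content of the rule is a clinical decision for the sponsor, and this review does not favour either version.

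SAP deviation C3 already carries an alternative-cause exception and needs changing only if the reconciled rule departs from footnote 5.

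The cost is a few lines in a protocol amendment. No new data, assessments or analyses are needed.

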#### 3.3.4.2 Recommendation to discontinue nintedanib

In the following cases discontinuation of nintedanib is highly recommended. Only in special circumstances, the investigator, upon thorough assessment of all available clinical data and taking into consideration the potential risks associated with administration of nintedanib, may decide not to withdraw the trial medication, even though one or more of the below mentioned criteria are fulfilled. In such a case, continuation of treatment with trial medication should be discussed with the patient, and the decision and reasoning documented in the source data.

- Major surgery, including any abdominal or intestinal surgery.
- Anti-coagulation. Patients who require full-dose therapeutic anticoagulation (e.g. vitamin K antagonists, heparin, hirudin, direct thrombin inhibitors, etc.), or high-dose antiplatelet therapy. (Prophylactic low dose heparin or heparin flush as needed for maintenance of an indwelling intravenous device (e.g. enoxaparin 4000 I.U. s. c. per day), as well as prophylactic use of antiplatelet therapy (e.g. acetyl salicylic acid up to 325 mg/day, or clopidogrel at 75 mg/day, or equivalent doses of other antiplatelet therapy is allowed.).
- Major thrombo-embolic events e.g. stroke, deep vein thrombosis, pulmonary embolism, myocardial infarction.
- Confirmed severe hypertension, uncontrolled under treatment ( $\geq 160/100$  mmHg),
- Unstable cardiac angina
- Increased risk of bleeding e.g. hemorrhagic CNS event, gross / frank haemoptysis or haematuria, active gastro-intestinal bleeding or GI-ulcers.

- Scleroderma renal crisis
- Significant pulmonary hypertension defined by any of the following:
  - Previous clinical or echocardiographic evidence of significant right heart failure
  - History of right heart catheterisation showing a cardiac index  $\leq 2$  l/min/m^2
  - PH requiring therapy (parenteral or oral with epoprostenol, treprostinil, selexipag)

For conditions that allow treatment interruption please refer to [Section 4.2.1](#).

